## 6.6 Treatment failure

Participants in the intervention arm with treatment failure, defined as positive HCV RNA PCR at end of treatment or post-treatment week 4, will be referred to a specialist office for further management of their HCV.

## 6.7 Hepatitis C Reinfection

Participants treated in the intervention arm who develop HCV reinfection as defined in section 5.5 will be referred to a specialist office for management of their HCV.

## 6.8 Incident hepatitis C infection

Participants with incident hepatitis C as defined in section 5.6 will be given options for treatment of their HCV. These may include enrollment in other studies (if eligible) or referral to an external provider for management of their HCV.

## 6.9 Drug Interactions

Participants will be assessed for the following drug interactions based on commonly observed co-administered medications: H2-receptor antagonists in doses exceeding famotidine 40mg twice daily, proton-pump inhibitors in doses exceeding omeprazole 20mg daily, amiodarone, digoxin, topotecan, phenytoin, phenobarbital, carbamazepine, oxcarbazepine, rifampin, rifapentine, rifabutin, St John's Wort, rosuvastatin at doses exceeding 10mg. Where alternatives can be found, they will be utilized in

conjunction with the prescribing provider. Participants with treatment-limiting drug interactions for which no alternative can be found will be excluded from study and referred to HCV treatment specialists off-site.

#### 6.10 Storage and distribution of medications

Medications will be stored at the treatment site for immediate dispensation to enrollees as described above. These will be stored in a combination locked safe, for a maximum of 2 months, with temperature maintained below 30 deg C as detailed in the package insert.

### 7 Criteria for discontinuation

#### 7.1 HCV treatment discontinuation

Participants in the intervention arm who discontinue HCV treatment prematurely for any reason will remain in the study. If more than 5 consecutive days of study medication were missed, the study investigator will advise treatment be held and offer HCV RNA testing. Based on these results, the study investigator will determine if re-initiation and completion of treatment should occur.

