#### 1.4.2 Intervention Arm

In Part A: Participants randomized to the intervention arm will have a same-day visit with a study physician. Those who are interested in being treated for their HCV, and have no contraindication, will (a) have standard of care baseline laboratory testing drawn and be given a one-week ‘Starter-Pack’ (7 day supply) of sofosbuvir 400mg/velpatasvir 100mg. Subsequent supplies of DAA therapy will be distributed to HCV RNA test positive participants as one 21-day and one 56 day supply to complete a 12-week treatment course. Those participants with negative confirmatory HCV RNA testing will be contacted via telephone and instructed not to begin the medication, and will not be given additional medication supplies.

Participants will be contacted weekly while receiving sofosbuvir/velpatasvir by text message to assess adherence, potential adverse effects, and offered other tele-support as needed. Scheduled study visits will occur at 4 weeks, upon treatment completion or discontinuation (study week 12), study week 16 (corresponding to SVR4), study week 24 (corresponding to SVR12), study week 36, and study week 48. Each study visit will consist of laboratory testing, semi-structured interview, and physician visit. Additional medical visits may be scheduled at the participants’ request. Additionally, each participant will be scheduled for a one-time counseling session for prevention of reinfection during their course of treatment. Referral to harm reduction and/or opioid substitution treatment programs will be provided for interested participants, but utilization of these services is not a condition of enrollment in the study or of HCV treatment provision.

In Part B: Participants will be enrolled in the telemedicine arm, and will have a same-day or next-day telemedicine visit with the hepatitis C provider. Initial evaluation will be either via telephone, video, or in-person at the syringe service program depending on patient preference. Blood testing will be arranged at local community laboratory facilities. Participants with positive HCV RNA will have delivery of a 28 day supply of sofosbuvir/velpatasvir, and a 56 day supply after completion. Weekly check-ins will occur by phone, and participants will have clinical laboratory monitoring at week 4 (optional), week 12, every 12 weeks thereafter until completion of follow up. Participants will complete a short structured survey at weeks 0, 12, 24, 36, and 48, also over video or telephone.

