### 3.0 Study Design

This is a single-center, open-label, randomized controlled trial, in which 72 HCV antibody positive participants between ages 18-29 will be recruited in two parts. During Part A, participants will be randomized to either the rapid treatment intervention arm, or the usual care control arm. During Part B, participants will be enrolled to the telemedicine arm. Recruited individuals must have used injection drugs in the past 30 days, have no medical contraindication to sofosbuvir and velpatasvir treatment, be HIV uninfected, and be HCV treatment naïve. During part B, they must have access to technology that allows telemedicine interventions (eg telephone, smartphone, or internet connection).

The goal of the study is to provide same-day, easily accessed medical evaluation and treatment to the intervention arm. During part A, participants randomized to the intervention will receive medical evaluation, laboratory assessment including confirmatory HCV RNA testing, baseline questionnaire/interview, and distribution of a 7-day medication “starter pack” on the day of enrollment. Participants who are HCV RNA negative will be notified by phone call, be asked to return their medications but continue to be followed for research visits every 12 weeks, similar to the control-arm. During part B, participants will have the option of an in-person evaluation at the syringe service program or a telemedicine visit on the day of enrollment or the following day. They will receive community based laboratory testing at a location that is convenient to them, and participate in study interview.

During part A, HCV RNA positive participants in the intervention arm will be asked to start medications, and return to pick up an additional 21-day supply. They will receive weekly text messages during treatment to record adherence. They will receive one follow-up medical visit at 4 weeks with laboratory evaluation, with distribution of the remainder of medications, and another visit at the end of treatment. One of these two visits (the participants’ choice) will include counseling for prevention of reinfection. They will then have HCV RNA PCR testing at end of treatment and 12 weeks post treatment, and at 48 weeks to assess for reinfection. Each study visit will include a brief questionnaire and qualitative interview.

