## 5 Study Procedures

### 5.1 Schedule of Events during Part A:

	Screening (performed by parent study)	Entry		On-Treatment				Post-Treatment								Additional tests if Treatment interruption	Additional tests if Reinfection or Relapse
		Week 0		Week 4		Week 12		Week 16		Week 24		Week 36		Week 48			
Randomized Arm		Int.	Con.	Int.	Con.	Int.	Con.	Int.	Con.	Int.	Con.	Int.	Con.	Int.	Con.		
HCV Antibody	X																
Plasma HCV RNA PCR		X	X	X		X	X	X		X	X	X	X	X	X		
HIV-1/2 Antibody	X									X	X			X	X		
Hepatic Function Panel		X		X†		X†				X†				X†			
Hematology (CBCC)		X								X†							
Basic Metabolic Panel		X		X†													
Weight		X															
FIB-4 (calculated)		X															
Hepatitis B panel		X															
Pregnancy Test (female participants)		X		X*†		X*†											
HCV genotyping		X														X†	
Physical Exam		X		X*†		X*†											
Adherence Assessment				Weekly for Int. arm†													

Reinfection Prevention counseling				Once for int. arm †												
Questionnaire and Interview		X	X			X	X		X	X	X	X	X	X		
Stored serum / plasma**		X	X			X	X	X	X	X	X		X	X		X

\*If medically indicated

\*\*In event phlebotomy is unavailable or unsuccessful, dried blood spots may be obtained by finger stick

† HCV RNA PCR Positive participants only

Windows: week 4 has a window of -7 days or + 14 days; Week 12 and 16 have a window of +7 days. Weeks 24 and 36 have a window of -14 to +28 days, and Week 48 has a window of -14 days.

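### Part A's supply timing and week-4 window allow a drug gap long enough to meet the section 7.1 hold rule; Part B's resupply wording allows a gap that cannot be sized

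*Combined protocol and SAP*

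**What the plan says.** **Part A supply.** Section 1.4.2 gives a 7-day starter pack at enrolment and then: "Subsequent supplies of DAA therapy will be distributed to HCV RNA test positive participants as one 21-day and one 56 day supply". Under section 3.0 participants "return to pick up an additional 21-day supply", with no day stated for that step. The rest comes later, at "one follow-up medical visit at 4 weeks with laboratory evaluation, with distribution of the remainder of medications".

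**Visit window.** The notes to the Part A schedule (section 5.1) state that "week 4 has a window of -7 days or + 14 days". The Part B schedule (section 5.2) repeats this window.

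**Hold rule.** Section 7.1 reads: "If more than 5 consecutive days of study medication were missed, the study investigator will advise treatment be held". HCV RNA testing is then offered, and the investigator decides whether treatment resumes. The section does not separate doses a participant skipped from doses that were not available.

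**Part B supply.** Under section 1.4.2, RNA-positive participants "will have delivery of a 28 day supply of sofosbuvir/velpatasvir, and a 56 day supply after completion". No time limit for the second delivery is stated. Section 3.0 describes the Part B visit schedule as similar to Part A's, with optional week-4 laboratory tests and all visits offered by telemedicine.

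**Starting point of the visit clock.** Section 2.2.3 counts the week-4 visit from the start of medication, which follows review of laboratory results. The schedule tables label entry as week 0.

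**The concern.** The supply handed out before week 4 in Part A runs out on the nominal visit day, so every day by which the visit is late is a day without drug. The window tolerates more lateness than section 7.1 tolerates interruption. A site could therefore follow the schedule exactly and still produce an interruption that the protocol treats as grounds for a hold.

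Two things are at stake. One is patient safety: the interruption would come from the supply plan and not from the participant. The other is interpretation. Treatment completion is a secondary outcome and adherence is to be described in the intervention arm. If days without supply are not recorded, a gap caused by resupply timing looks the same as a participant who stopped taking the drug.

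**Working it through.** **The plan's own figure.** Part A: 7 + 21 + 56 = 84 days. Part B: 28 + 56 = 84 days. Both reproduce the stated 12-week course.

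**Inputs for Part A.** Supply before the week-4 visit: 7 + 21 = 28 days (sections 1.4.2 and 3.0). Permitted visit days: 28 − 7 = 21 to 28 + 14 = 42 (section 5.1). Hold rule: more than 5 consecutive missed days, that is, 6 or more (section 7.1).

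**Assumptions.** One dose is taken each day from the first dose, the 21-day supply is collected without a break, and dosing resumes on the day of the visit.

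**Clock from first dose (section 2.2.3).** Days without drug = max(0, visit day − 28).

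| Visit | Day | Days without drug | Hold rule met |
|---|---|---|---|
| −7 | 21 | 0 | no |
| 0 | 28 | 0 | no |
| +5 | 33 | 5 | no |
| +6 | 34 | 6 | yes |
| +10 | 38 | 10 | yes |
| +14 | 42 | 14 | yes |

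Visits at +6 to +14 meet the rule. These are 9 of the 22 permitted days. That is a count of calendar days, not a probability.

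**Clock from entry (week 0 in the schedule table).** If the first dose is d days after entry, supply ends at day d + 28. The longest in-window gap is 42 − (d + 28) = 14 − d. The documents do not state d, so a range is needed: d = 0 gives 14 days, d = 7 gives 7, d = 8 gives 6, and d = 9 gives 5. On this clock the rule can be met for any d of 8 days or less, and not for d of 9 or more.

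**Effect on visit timing.** Suppose the clock runs from first dose, resupply is on day 42 and dosing resumes at once. The course then ends at day 42 + 56 = 98. The last permitted week-12 visit is day 84 + 7 = 91, so the end-of-treatment sample could be taken on treatment. Twelve weeks after treatment is day 98 + 84 = 182, inside the week-24 window (168 − 14 = 154 to 168 + 28 = 196) but later than the nominal day 168.

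**Part B.** If the 56-day supply arrives g days after the first 28 days run out, the gap is g days, and the rule is met when g is 6 or more. Nothing in the current text bounds g or expressly links the delivery to the week-4 visit, so no figure can be given.

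**The 7-day to 21-day step in Part A.** A gap is possible here too, but no day or window is stated, so it cannot be computed.

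**The case against.** The best defence is that the passages can all be followed together. The visit is planned for four weeks, when the supply ends. The 14 days are a tolerance for lateness, and section 7.1 is the contingency if a gap occurs, with the participant staying in the study. That stands to this extent: a reader might infer that the passages flatly contradict each other, and they do not. What remains is that the tolerance is wider than the interruption limit, and nothing written keeps one inside the other.

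There are mitigations. Section 1.4.2 has weekly adherence texts, tele-support and visits on request. Section 2.2.3 allows extra visits when staff judge them necessary. Section 6.10 keeps drug at the treatment site, and the window allows an early visit. Any of these could prevent a gap in practice, but none carries a resupply rule or deadline.

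The second defence is that Part A is analysed on enrolment through March 1, 2020, and continued enrolment is into Part B, where the week-4 window does not govern resupply. This is correct and limits the point. The phrase on the second Part B supply may only give the order of the two deliveries. The amendment summary (section 0.2, item 2) has the final supply arranged at a telemedicine visit two weeks after delivery, which suggests lead time. The current body text states no such lead time.

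The third defence is that the trial tests a delivery model, so interruptions from its own logistics belong in its result. This stands in full. A reader might infer that such failures are unfairly counted against the arm and should be removed. The intention-to-treat analysis in section 8.3.1 does not support that.

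**Conclusion.** The point holds for Part A as a possibility built into the written plan. An in-window week-4 visit can follow up to 14 days without drug if the visit is counted from first dose, or 14 minus the start delay if counted from entry, against a limit of 5 in section 7.1. It rests on daily dosing, no break at the 21-day pick-up, and the absence of any written bridging supply.

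For Part B, a gap is possible because the second delivery has no time limit and the visit schedule and window are carried over. A reader might apply the Part A day counts to Part B, but they depend on handing out drug at the week-4 visit, which the documents state only for Part A.

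Two further inferences go too far. The documents give no data on visit timing, so no share of participants can be stated. Section 2.3 lists resistance as a risk after treatment failure, but no passage says that a supply gap of this length causes failure. Nor is SVR12 necessarily lost: RNA is also tested at weeks 36 and 48, and the primary outcome runs to week 48.

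This should be corrected before further Part B dosing. It does not undermine the primary comparison.

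**What to change.** For participants still to be treated, reconcile sections 1.4.2 and 3.0, the week-4 window and section 7.1, so that a visit or delivery within the permitted time cannot by itself trigger the hold rule. The sponsor's clinicians should decide which passage changes; this review proposes no clinical rule.

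State whether the week-4 window counts from entry or from first dose.

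Record days without supply separately from missed doses. For Part A, derive them from dispensing dates if these were recorded. Use them to help interpret adherence and completion, and leave the intention-to-treat result unchanged.

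The cost is protocol wording for Part B, one extra data field, and a look at existing Part A dispensing dates where available. No change to sample size or to the primary analysis is needed.

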#### 7.2 Study withdrawal and discontinuation

Participants may be withdrawn from the study at any time at their own request. They may also be discontinued from the study if, at any time, they are considered by study investigators to be unlikely to be able to participate in necessary follow up (e.g. due to severe illness, incarceration, change of residence). However, in keeping with the overall goal of the intervention, participants who are unwilling to partake in interviews or questionnaires, or undergo blood tests, will still remain in the study.

### 8 Statistical and analytic considerations

#### 8.1 Sample size

Our own data (and others) suggests a SVR12 rate of 85% in active PWID (30), and existing literature suggests the control arm will have a very low uptake of HCV treatment (12% initiate treatment). (16) Using these estimates and an alpha =0.05, we have 100% power to detect a difference. However given the available referral and linkage programs, the control arm may have better HCV uptake and SVR 12 rates than predicted by literature. Assuming 41% (11/27) of participants in the control arm achieve SVR12, we will have 80% power to detect an SVR of 78% in the intervention arm.

In addition to have an adequate sample size to compare the primary end point of SVR12 rates with the control arm, a sample size of 27 HCV infected participants in Rapid Treatment arm allows for 90% power to show with reasonable certainty that the underlying true SVR12 rate is greater than 60% in the Rapid Treatment arm, assuming that this true rate is actually 85%.

The table below also shows two-sided exact Blyth-Still-Casella (BSC) 90% CIs for potential observed SVR proportions for 27 enrolled participants. With a HCV infected sample size of 27 participants, the CI for the true SVR12 rate will be entirely above 60% if 21 or more of the 27 participants achieve SVR12.

Patients enrolled and found not to have detectable HCV RNA will be replaced. Assuming 75% of HCV antibody positive individuals will be infected with HCV (positive HCV RNA), we anticipate have to enroll roughly 36 participants in each arm to acquire 27 with confirmed viremia.

Observed SVR12 Rate	90% CI for True SVR12 Rate
85% (23/27)	(71%, 93%)
81% (22/27)	(65%, 90%)
78% (21/27)	(62%, 90%)
74% (20/27)	(58%, 85%)
70% (19/27)	(54%, 84%)
67% (18/27)	(50%, 80%)

As of this amendment, data from part A will be analyzed based on enrollment through March 1 2020, so the power to detect a difference will be reduced from the above calculation. This is due to the break in enrollment that was necessary during the COVID-19 pandemic.

## 8.2 Randomization

Participants will be randomly assigned to the intervention or control condition in a 1:1 ratio using randomly permuted blocks. Participants randomized in the intervention arm will receive medical evaluation and distribution of “starter pack.” Participants in the control arm will be provided referral to community HCV providers.

## 8.3 Data Analysis

### 8.3.1 Analysis of clinical outcomes data

For the primary analysis, after the completion of part A, we will compare the proportion of patients who achieve SVR12 in each arm using Chi-square or Fishers’ exact testing, using an intention-to-treat approach in which participants are analyzed in the group to which they are randomized. Participants with negative confirmatory HCV RNA PCR tests on study entry will not be included in the analysis.

For secondary analyses, we will:

- Compare the proportion of patients who achieve end-of-treatment response using Chi-square or Fishers’ exact testing
- Compare the proportion of patients who complete treatment, using Chi-square or Fishers’ exact testing
- Compare the proportion of patients who have HCV reinfection, using Chi-square or Fishers’ exact testing
- Describe adherence for participants in the Intervention arm only
- Describe demographic, clinical and behavioral factors for participants who have HCV reinfection or incident HCV infection

We will also perform the same analyses using an “as-treated” approach, in which participants in the intervention arm will not be included if they failed to initiate HCV treatment, or discontinued treatment for reasons clearly unrelated to the treatment intervention (e.g. relocation, incarceration).

After the completion of part B, we will compare the proportion of patients who achieve SVR12 in each Part B telemedicine to (1)Part A intervention (2) Part A control, using Chi-square or Fishers’ exact testing, using an intention-to-treat approach in which participants are analyzed in the group to which they are randomized. Participants with negative confirmatory HCV RNA PCR tests on study entry will not be included in the analysis.

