#### 1.5 Hypothesis

We hypothesize that the ST&RT intervention will be accepted by HCV infected PWID aged 18-29, and lead to higher rates of treatment initiation, completion and SVR12 compared to the usual practice of referral to community HCV providers.

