Participants in the control arm will be provided facilitated referral to community HCV providers by an on-site care coordinator already facilitating care at the community site. HCV RNA negative participants will be called to inform them of these results, and then discontinued from the study. HCV RNA positive participants will be asked during the semi-structured interviews as at 12, 24, 36 and 48 week if they engaged in HCV treatment to assess whether their HCV referral has been filled, and to record their current HCV treatment status. They will also receive repeat HCV RNA testing at week 12, 24, and 48. Participants that have started treatment will be asked to sign consent for release of medical records pertaining to HCV-related laboratory testing to determine achievement of treatment response.

During part B, HCV RNA positive participants will have a 28-day supply of medications delivered, or available for pickup, as they prefer. The schedule of visits will be similar except that laboratory testing at week 4 will be optional, and all visits will be offered through telemedicine.

The three arms will be compared for the main outcome of SVR12 using a modified intention to treat analysis in which participants will be analyzed in the group they are randomized except for those who are (a) discontinued due to HCV RNA negative status or (b) found to have previously undiagnosed HIV at enrollment. Secondary outcomes will be compared using the same modified intention to treat design.

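### The as-treated rerun drops non-starters and unrelated stoppers from the intervention arm only, so its between-arm tests favour the intervention by construction

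*Combined protocol and SAP*

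**What the plan says.** The primary analysis in section 8.3.1 compares SVR12 between the Part A arms as randomised, leaving out participants who were RNA-negative at entry. Secondary analyses compare end-of-treatment response, completion and reinfection with the same tests. Section 3.0 adds: "Secondary outcomes will be compared using the same modified intention to treat design".

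Section 8.3.1 then says "We will also perform the same analyses using an" as-treated approach, and defines it by one exclusion: "participants in the intervention arm will not be included if they failed to initiate HCV treatment, or discontinued treatment for reasons clearly unrelated" to the intervention, with relocation and incarceration as examples. No section gives a usual-care counterpart.

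The plan foresees intervention participants who do not start or do not finish:

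- Section 1.4.2 offers medication to "Those who are interested in being treated for their HCV, and have no contraindication".
- Section 5.5 schedules RNA tests for participants left untreated for reasons other than negative RNA status.
- Section 6.4 keeps in the study, untreated, those found pregnant before starting.
- Section 7.1 keeps early stoppers in the study.

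**The concern.** Section 1.6 defines SVR12 from the end of treatment, so someone who never starts cannot achieve it. The same holds for end-of-treatment response and completion. Removing non-starters from one arm removes certain failures from one denominator. The contrast then sets cure among intervention starters against cure among everyone referred.

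Initiation is also a post-randomisation outcome that the intervention is meant to change: section 1.5 expects it to "lead to higher rates of treatment initiation, completion and SVR12 compared to the usual practice". Filtering on initiation in one arm erases that arm's own uptake failures while still charging usual care for its failures.

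What is at stake is the reading of the as-treated p-value. Enrolment to Part A was cut short, and section 8.1 says power will be reduced, so an inconclusive primary result is more likely than planned. A significant as-treated result beside it could be a product of the exclusion rule.

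**Working it through.** **Inputs from the documents.** 27 RNA-positive participants per arm; alpha 0.05; SVR12 of 85% in active PWID; and "Assuming 41% (11/27) of participants in the control arm achieve SVR12" (all section 8.1).

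**Assumptions.** The 85% is used as the cure rate among starters. Intervention initiation and unrelated-stop rates and the final Part A size are not given, so they are varied.

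**Plan's own figure.** 11/27 against 21/27 with 27 per arm, two-sided 0.05: power is 80.9% by the normal approximation. Exact enumeration gives 80.1% (uncorrected Chi-square) and 72.0% (Fisher). The stated 80% reproduces.

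**Algebra for non-starters.** With x responders among n, of whom k never started, x/n becomes x/(n − k), which is larger whenever x and k exceed 0. With initiation q and cure among starters c, the full-arm rate is qc and the filtered rate is c, so the shift is c − qc = c(1 − q).

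**False-benefit rate with identical arms.** Kept intervention n ~ Bin(27, q), responders ~ Bin(n, c); usual-care responders ~ Bin(27, qc) over 27. A false benefit is p < 0.05 in favour of the intervention. The last column counts only cases where intention-to-treat on the same data shows no significant benefit. Here c = 0.85.

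| q | Expected SVR12, intervention vs usual care | Shift (points) | False benefit, Chi-square / Fisher | With ITT not significant |
|---|---|---|---|---|
| 80% | 85% vs 68% | 17 | 27.3% / 21.4% | 24.6% / 20.1% |
| 90% | 85% vs 76.5% | 8.5 | 11.5% / 7.1% | 8.7% / 6.0% |
| 92% | 85% vs 78.2% | 6.8 | 9.2% / 5.1% | 6.4% / 4.0% |
| 95% | 85% vs 80.75% | 4.25 | 6.3% / 2.7% | 3.5% / 1.8% |
| 100% | 85% vs 85% | 0 | 2.8% / 0.7% | 0 |

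**Sensitivity to c.** At 90% initiation, c = 0.75 gives 8.8% / 6.1% and c = 0.95 gives 18.8% / 6.8%.

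**Sensitivity to arm size (c = 0.85).** For 12, 18 and 22 per arm:

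- 80% initiation: 13.7% / 7.4%, 18.5% / 13.8%, 23.0% / 16.5%.
- 90% initiation: 6.3% / 2.5%, 8.4% / 5.3%, 9.8% / 6.6%.

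**Unrelated stoppers.** If everyone starts, a share s stop and respond at rate r, and those kept respond at rate c, the shift is c − [(1 − s)c + sr] = s(c − r). For SVR12 with s = 0.10 and c = 0.85:

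- r = 0: 0.10 × 0.85 = +8.5 points
- r = 0.5: 0.10 × 0.35 = +3.5 points
- r = 0.85: 0
- r = 1: 0.10 × (−0.15) = −1.5 points

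So the direction for SVR12, and likewise for end-of-treatment response, depends on how the stoppers fare. For completion r = 0 by definition. If 90% of those kept complete, the shift is 0.10 × 0.90 = +9 points and the false-benefit rate is 14.1% / 7.3%.

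**Worked example.** Against usual care at 11/27:

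- 18/27 by intention to treat: p = 0.056 (Chi-square), 0.10 (Fisher).
- Two of the nine failures never started, so 18/25 (72%) as-treated: p = 0.023, 0.029.

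**The case against.** The strongest reply is that this is a supplementary analysis. The primary test is intention-to-treat, section 3.0 puts the secondary comparisons under modified intention-to-treat, and no section rests a conclusion on the as-treated rerun. That is right, and it limits the severity.

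Second, identical arms with 80–95% starting do not resemble the expected usual-care arm, for which section 8.1 cites 12% uptake or, cautiously, 41% SVR12. In those scenarios the primary test usually settles the matter: 21/27 against 11/27 gives p = 0.006 (Chi-square) or 0.012 (Fisher). This is fair as to the false-positive rates. But the shift c(1 − q) depends only on the intervention arm, so a real benefit would be overstated by the same amount.

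Third, the relevant risk is a discordant result, whose probability is 1 to 3 points below the headline rates. The last column of the table gives it.

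Fourth, the worked example lies near the threshold. With one non-starter (18/26) Fisher gives 0.054, and 17/25 gives 0.058. It shows that two participants can change the result, not that they typically would.

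Fifth, the reinfection comparison, also among the repeated analyses, should not be moved by dropping non-starters. Section 1.7 bases it on those with SVR12 or RNA-negative at baseline.

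Finally, the rule is pre-specified, and a summary of results in those actually treated is a reasonable aim. That supports describing the treated intervention participants. It does not support testing them against an unfiltered usual-care arm.

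**Conclusion.** The concern holds and should be fixed. The exclusion as written biases the as-treated SVR12, end-of-treatment response and completion contrasts toward the intervention whenever some intervention participants do not start. Dropping unrelated stoppers always raises completion further when there are any; its effect on the two response outcomes can go either way.

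The size depends on an initiation rate that the documents do not give. Under the assumptions above it runs from nothing at full initiation with no unrelated stopping, through about 4 points at 95%, to 17 points at 80%. The primary analysis, the modified intention-to-treat secondary comparisons and the Part B comparisons are unaffected. What changes is whether the as-treated p-value can support any claim about the arms; as the rule stands, it cannot.

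**What to change.** In section 8.3.1, state that the intention-to-treat and modified intention-to-treat comparisons are the only tested between-arm contrasts, and do not test the contrast filtered in one arm. Report as-treated results descriptively, either for the intervention arm alone or among initiators in both arms. Label them non-randomised, because starting treatment happens after randomisation. If unrelated stoppers are excluded, exclude them in both arms, and only where usual-care reasons for stopping are known; otherwise keep them in both.

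The cost is one or two sentences. Usual-care initiators can be identified from data already planned: section 3.0 has usual-care participants asked "if they engaged in HCV treatment to assess whether their HCV referral has been filled, and to record their current HCV treatment status". No section shows that their reasons for stopping are collected, so excluding stoppers in both arms would need that item added; retaining them would not.

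There are two downsides. The supplementary result will look less favourable to the intervention. A both-arm description may also be imprecise: at the cited 12% uptake, about 27 × 0.12 = 3.2 usual-care participants would have started.
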